#### 4. PROTOCOLS FOR CONTROLLED OVARIAN STIMULATION AND LABORATORY PROCEDURES

The patient population of this trial is unique and rather homogenous; this represents a precious opportunity to study different parameters related to fertility, pregnancy and also breast cancer biology. As a part of signing the study informed consent and their participation in this study, patients consent to perform the examination specified in Table 1.

**Table 1. Schedule of assessment for correlative research**

	Inclusion (diagnosis)	M 0-1 (start of COS)	M 0-1 (end of COS)	M4-6 (end of CT)	M 16-18 (12 M after CT)	M 28-30 (24 M after CT)	M 60 (5 y after diagnosis)	Relapse
Serum (AMH, FSH, E2)	x			x	x	x	x	
Serum (Progesterone/E2)		x*	x**					
Plasma for ctDNA	x		x					x
Whole blood	x							
1 block of FFPE of primary tumor s	x							

x: mandatory

\$: 15 representative slides of 10 µm should be provided.

\*: Can be performed at the inclusion if COS start within 5days

\*\* : serum samples at L3 and L8 will be collected

#### 4.1. Schema of the two controlled ovarian stimulation protocols

##### 1) Letrozole-stimulated breast cancer cohort

There are a few options to start letrozole-associated controlled ovarian stimulation, depending on the cycle phase at the time of patient referral for fertility preservation.

During early follicular phase, letrozole is usually administered on the second day of menstruation. The controlled ovarian stimulation (recombinant FSH or HMG, 75-300 IU/d) is started the following day. GnRH antagonist is added to the controlled ovarian stimulation at day 7 or when the leading follicle reaches 12-14 mm and/or when estradiol reaches 250 pg/ml to prevent premature luteinizing hormone (LH) surge. In the late follicular phase, controlled ovarian stimulation with letrozole can be started before ovulation or ovulation can be induced with GnRH $\alpha$ , before starting controlled ovarian stimulation.

During the luteal phase, antagonist may be administered for a few days before controlled ovarian stimulation to induce luteolysis, or controlled ovarian stimulation can be started at the same time as letrozole, and antagonist will be added when leading follicle has reached 12-14 mm.

In all situations, GnRH agonist (Décapeptyl or Gonapeptyl 0.2 mg) is used for ovulation trigger when at least 3 follicles reach 18 mm.

## 2) Standard-stimulated breast cancer cohort

[figure not shown]
During early follicular phase, controlled ovarian stimulation is started on the second-third day of the cycle (with recombinant FSH or HMG, 75-300 IU/d). GnRH antagonist is added to the controlled ovarian stimulation at day 7 or when the leading follicle reaches 12-14 mm and/or when estradiol reaches 250 pg/ml to prevent premature LH surge. In the late follicular phase, controlled ovarian stimulation can be started before ovulation or ovulation can be induced GnRH $\alpha$ , before starting controlled ovarian stimulation.

During the luteal phase, antagonist may be administered for a few days before controlled ovarian stimulation to induce luteolysis, or controlled ovarian stimulation can be started, and antagonist will be added when leading follicle has reached 12-14 mm.

In all situations, GnRH agonists (Décapeptyl or Gonapeptyl 0.2 mg) are used for ovulation trigger.

**Random start protocol**

**Standard protocol**

**Figure.** Random-start or standard controlled ovarian stimulation protocols.

## 4.2. Laboratory procedures for oocyte/embryo cryopreservation

Oocytes and embryos are vitrified in the equilibration and vitrification solutions according to the manufacturer's instructions of the vitrification Vit Kit®-Freeze (Irvine Scientific, California) or Rapid-I-kit® (Vitrolife, Sweden). The oocytes/embryo are then loaded on in vitrification high security closed system (VHS, CryoBioSystem, France or mediprene straw RapidStraw, Vitrolife, Sweden) in a volume of <math><1\mu\text{l}</math>, and immediately submerged into liquid nitrogen.

During warming, the cryoprotectants are removed according to the manufacturer's instructions of the devitrification kit Vit Kit®-Thaw (Irvine Scientific, California) or devitrification Kit Rapid Warm (Vitrolife, Sweden).

## 4.3. Laboratory procedures for ovarian reserve and function biomarker analysis

This constitutes serum evaluation of anti-mullerian hormone (AMH), follicle stimulating hormone (FSH), estradiol (E2) and serum progesterone. Hormonal measurement for the study will be centrally performed at the LHUB (Laboratoire Hospitalier Universitaire de Bruxelles). Elecsys® AMH module (Roche Diagnostics, Vilvoorde, Belgium) is used for AMH measurement. Estradiol and progesterone are assayed by electrochemiluminescence immuno-assay using a competitive immunoassay (Modular E170—Roche diagnostics, Germany). The inter-assay coefficient of variation was less than 5% for all assays.

The evaluation of AMH, FSH, and E2 will be done at enrollment (i.e. at the time of oncofertility counseling/breast cancer diagnosis) before starting chemotherapy (and before starting controlled ovarian stimulation in patients who access oocyte/embryo cryopreservation). Then, these analyses will be repeated at the end of chemotherapy, 12 and 24 months after the end of chemotherapy, and finally 5 years after diagnosis. At all time points, a 5ml of blood sample should be collected. After blood clotting, each tube should be centrifuged at 2600g for 10 minutes and serum should be collected

in 1mL aliquots. For each sample, two 1mL aliquots are required. Aliquots should be stored at  $-80^{\circ}\text{C}$ . The aim of these analyses is to evaluate the impact of anticancer treatment on ovarian reserve (i.e. AMH) and ovarian function parameters (FSH, E2).

Serum progesterone and E2 will be evaluated the first day and at the end of controlled ovarian stimulation (trigger day). A 5ml of blood sample should be collected. After blood clotting, each tube should be centrifuged at 2600g for 10 minutes and serum should be collected in 1mL aliquots. For each sample, one 1mL aliquot is required. Aliquots should be stored at  $-80^{\circ}\text{C}$ .

All samples will be shipped to the central laboratory (Erasmus hospital) at fixed time points for analysis.

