### 3.2. Data collection

For all consecutive eligible patients included in the study, anonymized data will be entered into ad hoc electronic Case Report Forms (eCRF). The following information will be collected:

1) Baseline characteristics (at study inclusion): BMI; smoking habit; age at menarche; use of birth control pills; prior children before breast cancer diagnosis; history of spontaneous or induced abortion; prior treatment for infertility; prior gynecological surgery and/or medical history with possible impact on fertility; baseline AMH value.

- 2) Breast cancer history: date of diagnosis; age at diagnosis; disease stage; type of breast and axillary surgery; histology; tumor size and nodal status (for patients who underwent primary systemic therapy, both clinical tumor size and nodal status before treatment initiation and pathological tumor size and nodal status at the time of surgery will be collected); grade; hormone receptor status (estrogen and progesterone receptors); HER2 status.
- 3) Treatment of the primary tumor: timing of systemic therapy administration (adjuvant or neoadjuvant); use of chemotherapy (type and number of cycles); use of endocrine therapy (type and duration); use of anti-HER2 targeted therapy (type and duration); use of radiotherapy; use of breast reconstruction surgery.
- 4) Survival status: any recurrence of invasive breast cancer including date of the event; type of recurrence of invasive breast cancer (locoregional or distant event); any second primary contralateral breast cancer including date of the event; any second primary malignancy including date of the event; date of last follow-up and/or death.
- 5) Controlled ovarian stimulation protocol: type of stimulation (follicular or random); total FSH dose; number of stimulation days; number of days with antagonist; estradiol and progesterone levels at triggering and during luteal phase (L3-L8); number of oocyte/embryo collected; number of mature oocytes collected; maturation rate; number of oocyte/embryo cryopreserved; number of patients with poor response; number of patients with stimulation failure.
- 6) Ovarian function before and after chemotherapy: treatment-induced amenorrhea; age at menopause; AMH values.
- 7) Pregnancy after breast cancer: any pregnancy including date of the event; pregnancy outcome; gestational age at delivery; pregnancy/fetal/obstetrical outcomes; breastfeeding and its duration; use and type of assisted reproductive technology.

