To evaluate the safety of performing a controlled ovarian stimulation with or without letrozole in young women with newly diagnosed breast cancer who are candidates to receive (neo)adjuvant chemotherapy, the following endpoints will be assessed:

- Invasive disease-free survival (iDFS) defined as the time from study inclusion to the first appearance of the following invasive events: local recurrence, distant metastases, contralateral or ipsilateral breast tumor, second primary malignancy, or death from any cause;
- Breast cancer-free interval (BCFI) defined as the time from study inclusion to the first appearance of the following invasive events: local recurrence, distant metastases, contralateral or ipsilateral breast tumor;
- Overall survival (OS) defined as the time from study inclusion to death from any cause;
- Kinetic of circulating tumor DNA (ctDNA) assessed before, after stimulation and during study follow-up (if disease relapse).
- Complications associated with any of the procedure used for oocyte/embryo cryopreservation.

The safety of performing controlled ovarian stimulation with or without letrozole will be evaluated in various subgroups of young women with newly diagnosed breast cancer who are candidates to receive (neo)adjuvant chemotherapy according to the following characteristics:

- Stage at diagnosis: I vs. II vs. III;
- Hormone receptor status: positive vs. negative;
- HER2 status: positive vs. negative;
- Type of exposure to chemotherapy: prior to surgery (neoadjuvant) vs. post surgery (adjuvant);
- Exposure to endocrine therapy: exposure vs. no exposure;
- Presence of *BRCA* mutation: *BRCA*-mutated vs. *BRCA*-not mutated;
- Baseline ctDNA level: present vs. absent.

The following baseline characteristics of young women with newly diagnosed breast cancer who undergo controlled ovarian stimulation with or without letrozole will be assessed:

- Body-Mass Index (BMI) and body surface;
- Smoking history;
- Age at menarche;
- Prior pregnancies (completed, induced or spontaneous abortion);
- Prior treatment for infertility;
- Prior use of birth control pills;
- Prior gynecological diseases with potential impact on reproductive potential;
- Baseline ovarian reserve and function analysis.

Furthermore, the following characteristics of protocols with or without letrozole used for controlled ovarian stimulation in young women with newly diagnosed breast cancer who are candidates to receive (neo)adjuvant chemotherapy will be evaluated:

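### FSH and estradiol draws carry no cycle date, so in menstruating women the FSH/E2 part of the ovarian-function aim mixes treatment effect with cycle phase

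*Combined protocol and SAP*

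**What the plan says.** Section 4.3 gives the serial AMH, FSH and E2 measurements a purpose: "The aim of these analyses is to evaluate the impact of anticancer treatment on ovarian reserve (i.e. AMH) and ovarian function parameters (FSH, E2".

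The timing is by calendar. The first sample "will be done at enrollment (i.e. at the time of oncofertility counseling/breast cancer diagnosis) before starting chemotherapy"; after that, "these analyses will be repeated at the end of chemotherapy, 12 and 24 months after the end of chemotherapy", with a last one 5 years after diagnosis. Table 1 marks all five as mandatory. The instruction at the draw, "At all time points, a 5ml of blood sample should be collected", is followed by centrifugation and storage steps. No cycle day is set.

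Section 4.1 shows that women arrive at different points of the cycle. In the letrozole cohort the way stimulation starts varies, "depending on the cycle phase at the time of patient referral for fertility preservation", and the standard cohort also has early follicular, late follicular and luteal starts.

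Section 3.2 lists what is collected on ovarian function: "Ovarian function before and after chemotherapy: treatment-induced amenorrhea; age at menopause; AMH values". For stimulated patients it adds "type of stimulation (follicular or random); total FSH dose; number of stimulation days". Last menstrual period and cycle day appear nowhere in the list.

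Section 5 includes "Baseline ovarian reserve and function analysis" among the baseline characteristics of women who undergo stimulation. Its endpoints for the effect of anticancer therapy on ovarian function are amenorrhea, age at menopause and AMH; FSH and E2 are not among them.

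**The concern.** FSH and E2 depend on cycle phase in a woman who menstruates. The documents do not say how strongly, so the size is treated as unknown below. A value with no cycle date cannot be assigned to a phase, and a difference between two such values can come from a change in ovarian function, a change in phase, or both.

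Two uses are exposed: the before-and-after assessment of FSH and E2 in Section 4.3, and the baseline function description in Section 5. If phase at sampling is similarly distributed everywhere, the result is extra noise. If it differs between cohorts or between visits, it is bias. The two stimulated cohorts are defined by country, so different referral timing would look like a difference in function; the documents do not show that such a difference exists. A cycle date not asked for at the draw is hard to recover years later.

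**Working it through.** **1. The plan's own figure.** Section 5 sizes the study on mature oocytes: difference 1.5, SD 4.0, two-sided alpha 0.05, equal-variance t-test. d = 1.5/4.0 = 0.375. The noncentral t solution is n = 112.6 per group, rounded up to 113, with power 0.801 at 113. The stated figure reproduces. It does not concern FSH or E2, for which the documents give no effect size, SD or power.

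**2. What is known about phase at each draw** (Sections 3.2, 4.1, 4.3 and 5; Table 1).

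| Draw | Stimulated cohorts | Non-stimulated cohort |
|---|---|---|
| Inclusion | Partial: follicular or random start; first-day progesterone and E2 | None |
| End of chemotherapy | None | None |
| 12 and 24 months after chemotherapy | No phase; amenorrhea known at about these times | Same |
| 5 years after diagnosis | No phase; the amenorrhea endpoint is 5 years after chemotherapy | Same |

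The baseline markers are partial for two reasons. A random start does not separate late follicular from luteal. Both markers also describe the start of stimulation, and Table 1 lets that sample be taken at inclusion only if stimulation begins within 5 days. In the last row, chemotherapy ends at months 4 to 6, so the five-year amenorrhea endpoint falls at months 64 to 66 (60 + 4 to 60 + 6), against month 60 for the sample.

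**3. Count.** Planned patients: 113 + 113 + 339 = 565, of whom 339 (339/565 = 60%) are non-stimulated. With full attendance there are 565 × 5 = 2,825 draws. At most 113 + 113 = 226 have a phase marker: 226/2,825 = 8%. The other 2,599 (92%) have none. Some of these will be in women without periods, where phase is not a source of variation, so 92% is not the share of damaged values.

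**4. What the change estimates.** For a menstruating woman, write a value as function + phase + error. Then

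change = (function₂ − function₁) + (phase₂ − phase₁) + error.

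Without a cycle date the second bracket cannot be separated from the first. Let μₖ be the mean in phase k, and p₀ₖ and p₁ₖ the shares of samples in that phase in the two groups or at the two visits. The bias is Σₖ(p₁ₖ − p₀ₖ)μₖ, which is zero when the mixes agree. The documents give neither shares nor means, so the bias cannot be sized.

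**5. Loss of precision, on an assumed range.** Let phase make up a share f of the between-patient variance. A standardised effect d becomes d√(1 − f), and the required n is multiplied by 1/(1 − f). For scale only, take d = 0.375 with 113 per group:

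| f (assumed) | √(1 − f) | n multiplied by | Power |
|---|---|---|---|
| 0 | 1 | 1 | 80% |
| 0.2 | 0.89 | 1.25 | 71% |
| 0.4 | 0.77 | 1.67 | 59% |
| 0.6 | 0.63 | 2.5 | 43% |
| 0.8 | 0.45 | 5 | 24% |

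**6. How many undirected samples would be early follicular.** Assume draws spread evenly over a cycle of 26 to 32 days. Days 2–4 take 3/32 = 9.4% to 3/26 = 11.5%; days 2–5 take 4/32 = 12.5% to 4/26 = 15.4%. In a cohort of 113 menstruating women that is 113 × 3/32 ≈ 11 to 113 × 4/26 ≈ 17 samples.

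**The case against.** The strongest reply is that little depends on FSH and E2. Section 5 judges ovarian function by amenorrhea, age at menopause and AMH; Section 3.2 names AMH as the only hormone under ovarian function; and FSH and E2 sit in a schedule of correlative research. This stands, and it limits the point.

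Some stronger conclusions are tempting, but the documents do not support them:

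- **That the ovarian-function aim cannot be met.** The aim also covers AMH, and no listed ovarian-function endpoint uses FSH or E2. Section 4.3 assigns reserve to AMH, so it is also no criticism that off-phase FSH and E2 fail to measure reserve.
- **That phase is recorded nowhere.** Stimulated patients have the baseline markers above, and the Section 5 baseline list is about these women.
- **That every woman is cycling at inclusion.** Eligibility does not require it, and contraceptive pill use is collected.
- **That Table 1 leaves a two-month window for timing later samples.** Months 16–18 and 28–30 follow from chemotherapy ending at months 4–6, plus 12 or 24 months. No per-patient window is stated.

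Partial rescue is also possible. Recorded amenorrhea allows stratification at about the 12- and 24-month draws. Two serum aliquots are stored per draw, so progesterone, already a study assay, could be added later if serum remains. That would still be only a partial phase marker.

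What survives is narrower: Section 4.3 states an FSH/E2 aim, Table 1 makes five draws mandatory for it, and for most of them a menstruating woman's phase cannot be known.

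**Conclusion.** The point holds in limited form. In menstruating women, FSH and E2 and their change from baseline cannot be read as treatment effect alone, because sampling is not tied to the cycle and no cycle date is kept. This applies without mitigation to the non-stimulated cohort and to every post-chemotherapy draw, and in weaker form to stimulated patients at baseline. In women without periods it does not apply.

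The size is not known. The fall in power from 80% to between 71% and 24% rests on an assumed variance share of 20% to 80% and a borrowed effect size, and shows direction only. No bias is demonstrated; it would need phase mixes that differ between cohorts or visits.

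The primary endpoint, its sample size, AMH, amenorrhea and age at menopause are untouched. Because a correlative measure is concerned, this is a minor improvement, worth making because the missing item is cheap to collect at the draw and hard to recover afterwards.

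**What to change.** - **Record.** In Section 3.2 and Table 1, add two items at every FSH/E2 draw: the first day of the last menstrual period (or amenorrhea), and current hormonal treatment. The second should name GnRH analogues, because Section 5 admits their users to the non-stimulated cohort and Section 3.2 has no explicit item for them. Pill use and endocrine therapy are already collected, but not as status on the day of the draw.
- **Analyse.** State in Section 5 how FSH and E2 will be used: stratified by menstrual status and, in menstruating women, adjusted for cycle phase or restricted to early follicular samples. With so few undirected samples likely to be early follicular, restriction fits better as a sensitivity analysis at inclusion. Keep AMH as the reserve measure for everyone.
- **Schedule, optionally.** Where a site's calendar allows, the post-chemotherapy research sample may be taken in early follicular phase from women who menstruate. This should be presented as a matter of feasibility, not as use of an existing visit window.

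The cost is two eCRF fields per draw, a short addition to Section 5, and fewer FSH and E2 values that can be interpreted. No extra blood sample is needed.

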#### **4.4. Laboratory procedures for circulating tumor DNA**

Three blood samples of 10 ml should be collected in EDTA tubes; two samples will be centrifuged within 1 hour from collection, to separate plasma from peripheral blood cells, at 820g for 10 minutes at  $4^{\circ}\text{C}$ . Recover and transfer plasma (the top yellowish layer of the tube content) into new micro tubes, compatible with high-speed centrifuge. Centrifuge the plasma at maximum speed (if available 20000g is recommended) for 10 minutes at  $4^{\circ}\text{C}$ . Transfer all plasma into cryovials and stored at  $-80^{\circ}$ . The 3rd sample of whole blood will be stored directly at  $-80^{\circ}\text{C}$ . Blood and plasma samples will be shipped on dry ice to the central laboratory (Erasmus hospital) at fixed time points for evaluation.

Plasma samples will be collected at enrollment (i.e. at the time of oncofertility counseling/breast cancer diagnosis) before starting chemotherapy (and before starting controlled ovarian stimulation in patients who access oocyte/embryo cryopreservation), Then, this analysis will be repeated at the end of controlled ovarian stimulation, and at relapse or end of follow-up.

In this study, evaluation of the circulating tumor DNA (ctDNA) in the plasma will be performed. The aim is to 1) evaluate the effect of controlled ovarian stimulation on the levels of ctDNA and correlate

with risk of recurrence and 2) to evaluate the pattern of somatic mutations in young breast cancer patients.

Before performing the evaluation of ctDNA, primary tumor analysis is required. Hence, 15 representative slides (10µm) must be collected instead. Samples will be shipped to the central laboratory (Erasmus hospital) at fixed time points for evaluation.

The aim is to elucidate the biology of breast cancer in young women. Techniques will comprise but not restricted to immunohistochemistry, in situ hybridization, expression profiling and sequencing. Extraction of nucleic acids (DNA and RNA) may be required to perform these analyses.

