	
 
- To evaluate the characteristics of the ovarian stimulation cycle with or without letrozole in young women with newly diagnosed breast cancer who are candidates to receive (neo)adjuvant chemotherapy.
 
- To evaluate the efficacy of performing a controlled ovarian stimulation with or without letrozole in young women with newly diagnosed breast cancer who are candidates to receive (neo)adjuvant chemotherapy in terms of number of oocytes collected, maturation rate, number of oocyte/embryo cryopreserved, number of patients with poor response, and number of patients with stimulation failure.
 
- To evaluate the type and outcomes of assisted reproductive technology procedures in patients who return to the fertility clinic after the end of treatment. In patients with a clinically confirmed pregnancy obtained with assisted reproductive technology procedures after the end of treatment, pregnancy, fetal and obstetrical outcomes of the pregnancies will be evaluated.
 
- To evaluate the impact of anticancer therapies (chemotherapy with or without endocrine therapy with or without anti-HER2 agents) on patients' ovarian function.
 

Number of patients
	
A total of 113 patients are expected to be included in the standard-stimulated cohort, 113 in the letrozole-stimulated cohort, and 339 in the non-stimulated cohort (1:1:3).

Eligibility criteria
	
Inclusion criteria:
 
 
- Diagnosis of invasive non-metastatic breast cancer (i.e. stage I to III);
 
- Breast cancer diagnosis <math>\geq 18</math> and <math>\leq 40</math> years;
 
- No prior history of gonadotoxic treatments;
 
- Fertility preservation counseling for fertility preservation;
 
- Written inform consent;
 
- FSH <math>< 20</math> UI/L and/or antra-follicular count <math>\geq 6</math> (follicles of 2-9 mm) and/or AMH <math>\geq 6</math> pmol (only applicable for patients who undergo controlled ovarian stimulation for embryo/oocyte cryopreservation).
 
 
Exclusion criteria:
 
 
- Newly diagnosed stage IV breast cancer (i.e. de novo metastatic breast cancer);
 
- Prior diagnosis of other malignancies before breast cancer.
 

Design of the trial
	
Multicenter hospital-based prospective cohort study

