## 5. STATISTICS

Three cohorts of patients will be prospectively included in the study (Figure 1 in the Appendix):

**1) Letrozole-stimulated cohort:** this includes all newly diagnosed breast cancer who are candidates to receive (neo)adjuvant chemotherapy and undergo oocyte/embryo cryopreservation at the Belgian participating centres.

**2) Standard-stimulated cohort:** this includes all newly diagnosed breast cancer who are candidates to receive (neo)adjuvant chemotherapy and undergo oocyte/embryo cryopreservation at the French participating centres.

**3) Non-stimulated cohort:** this includes all newly diagnosed breast cancer who are candidates to receive (neo)adjuvant chemotherapy who have access to the Fertility Clinics in all the participating centres but are not willing to undergo oocyte/embryo cryopreservation. Patient who underwent another fertility preservation procedure (ovarian tissue cryopreservation, GnRH analogues,...) are eligible in this cohort.

All the efficacy analyses will be performed to compare the letrozole-stimulated cohort and the standard-stimulated cohort. All the safety analyses will be conducted to compare separately the letrozole-stimulated cohort with the non-stimulated cohort and the standard-stimulated cohort with the non-stimulated cohort.

To evaluate the efficacy of performing a controlled ovarian stimulation with or without letrozole in young women with newly diagnosed breast cancer who are candidates to receive (neo)adjuvant chemotherapy, the following endpoints will be assessed:

- Number of mature oocytes collected (primary endpoint).
- Number of oocytes collected;
- Maturation rate: defined as ratio between the number of mature oocyte collected and total number of oocyte collected;
- Number of oocyte/embryo cryopreserved;
- Number of patients with poor response: defined as retrieval of  $\leq 4$  oocytes;
- Number of patients with stimulation failure: defined as no follicular growth after 1 week of adequate controlled ovarian stimulation administration.

The efficacy of performing controlled ovarian stimulation with or without letrozole will be evaluated also in various subgroups of young women with newly diagnosed breast cancer who are candidates to receive (neo)adjuvant chemotherapy according to the following characteristics:

- Type of stimulation: follicular vs. random;
- Hormone receptor status: positive vs. negative;
- Presence of *BRCA* mutation: *BRCA*-mutated vs. *BRCA*-not mutated.

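### The change in ctDNA across ovarian stimulation has no planned comparator in the non-stimulated cohort, although Section 5 requires one

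*Combined protocol and SAP*

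**What the plan says.** Section 5 lists among the safety endpoints "Kinetic of circulating tumor DNA (ctDNA) assessed before, after stimulation and during study follow-up (if disease relapse"). It also sets the comparison: "All the safety analyses will be conducted to compare separately the letrozole-stimulated cohort with the non-stimulated cohort", and likewise for the standard-stimulated cohort. The non-stimulated cohort is made up of women who attend the fertility clinics but "are not willing to undergo oocyte/embryo cryopreservation".

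Section 4.4 gives the sampling. The baseline draw covers everyone: "Plasma samples will be collected at enrollment (i.e. at the time of oncofertility counseling/breast cancer diagnosis) before starting chemotherapy". For the later draws, "this analysis will be repeated at the end of controlled ovarian stimulation, and at relapse or end of follow-up". The first aim given there is to "evaluate the effect of controlled ovarian stimulation on the levels of ctDNA and correlate" it with the risk of recurrence.

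In Table 1 the row "Plasma for ctDNA" has three marks: inclusion, month 0-1 (labelled as the end of COS) and relapse. The synopsis plans 113 women in the standard cohort, "113 in the letrozole-stimulated cohort, and 339 in the non-stimulated cohort (1:1:3").

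**The concern.** The stated aim is causal: what stimulation does to ctDNA. To answer it, one needs the change that would have occurred over the same interval without stimulation. Section 5 points to the non-stimulated cohort for this, but the draw that would supply the value is defined by an event those women do not have.

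Without that value, what remains is a before/after change in stimulated women. It mixes any effect of stimulation with the course of the disease between diagnosis and chemotherapy, with breast surgery if it falls before or between the draws, and with assay variation. A rise could then be read as harm, or a flat result as reassurance, and neither reading would be supported. This bears on the safety question that Section 1 gives as a main reason for the study.

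**Working it through.** **The plan's own figure.** The plan gives no effect size, variance or sample size for ctDNA. Its one calculation concerns mature oocytes (difference 1.5, SD 4.0, two-sided alpha 0.05, power 0.80). An exact two-sample t-test gives 112.6 per cohort, rounded up to 113, with power 0.801 at 113. The figure reproduces and has no bearing on this point, which is checked by setting the sections side by side.

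**Step 1: which draws are defined for whom.**

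| Draw | Stimulated cohorts (113 + 113) | Non-stimulated cohort (339) | Source |
|---|---|---|---|
| Enrolment | Yes | Yes | Table 1, Section 4.4 |
| End of COS | Yes | No time defined | Table 1, Section 4.4 |
| Relapse | If relapse | If relapse | Table 1, Section 4.4, Section 5 |
| End of follow-up | Yes | Yes | Section 4.4 only |

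**Step 2: what the rule asks for.** Let Y0 be ctDNA at enrolment, Y1 ctDNA at the second draw, and D = Y1 − Y0. Applied to the early change, Section 5 asks for:

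- mean D (letrozole) − mean D (non-stimulated), planned 113 versus 339;
- mean D (standard) − mean D (non-stimulated), planned 113 versus 339.

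The second term is the same in both, and it needs a Y1 that the schedule does not define. No footnote to Table 1 and no sentence in Section 4.4 supplies one, such as a number of days after enrolment or a draw just before chemotherapy.

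**Step 3: what the remaining data can show.**

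- *Enrolment values* can be compared across all three cohorts, but they precede stimulation.
- *Relapse values* come only from women who relapse.
- *End-of-follow-up values* generally come after chemotherapy. Like the relapse values, they do not isolate stimulation.
- *D within a stimulated cohort* combines stimulation, disease course, surgery and assay variation. The baseline draw is at inclusion, not at the start of COS. A Table 1 footnote lets the COS-start hormone sample be taken at inclusion if COS begins within 5 days, so longer gaps are foreseen. No interval between the two plasma draws is fixed.
- *D in letrozole minus D in standard* can be estimated. It addresses the difference between protocols, not stimulation against none. Because the letrozole cohort is enrolled in Belgium and the standard cohort in France, it is also a comparison of countries.

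**Step 4: consistency of the last draw.** Section 4.4 schedules plasma at relapse or end of follow-up. Table 1 marks relapse only, and the endpoint in Section 5 mentions relapse only.

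**The case against.** **The rule in Section 5 may not be meant literally.** The objective speaks of ctDNA before and after stimulation, which can be read as a change within stimulated women. The same safety list includes complications of the cryopreservation procedure, which women without the procedure cannot have. This stands as evidence of loose wording. It does not remove the problem: a procedural complication can be attributed without a control group, but a change in ctDNA cannot, and no other ctDNA comparison is specified.

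**Table 1 may intend the sample for everyone.** The mark is mandatory, the column also reads month 0-1, the row is not limited by cohort, and Section 4 says patients consent to the Table 1 examinations. The ovarian-reserve criterion in Section 3.1 shows that the protocol can restrict an item to stimulated women when it wants to. This stands in part. A reader might infer that none of the 339 non-stimulated women will have a second early sample. The documents do not prove that. They show that no time is defined for it, so any sample a site happened to draw would not be a planned, time-matched comparator.

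**Much of the ctDNA work survives.** A reader might infer that no ctDNA comparison with the non-stimulated cohort is possible, or that the endpoint can tell nothing. Both go too far. Enrolment and late values remain comparable. Letrozole versus standard, the relation to estradiol at trigger, and the correlation with recurrence can all be studied.

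**Size.** It is tempting to compute how far untreated tumour growth alone would raise ctDNA between the draws. The documents give no growth rate and no interval. They include women treated with adjuvant chemotherapy and do not fix surgery relative to the draws; if the tumour has been removed, ctDNA may fall. No such figure is supportable.

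**Importance.** ctDNA kinetics is one of five secondary safety endpoints, and Table 1 is headed as correlative research. That is correct and limits the weight of the point.

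**Conclusion.** The point holds for the early change only. As written, Section 5 requires two comparisons with the non-stimulated cohort, and for the change from enrolment to end of COS neither has a planned comparator value, because Table 1 and Section 4.4 define the second draw by COS alone. This is more than a missing detail: a stated rule cannot be carried out for the core of a listed endpoint, and what is left is an uncontrolled before/after change set against an aim worded as an effect of stimulation.

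The conclusion rests on reading the column label and Section 4.4 as they stand. If the sponsor meant the month 0-1 draw for all cohorts, the fault is that its timing for non-stimulated women was not written down. No numerical magnitude is claimed. The primary endpoint, the sample size, iDFS, BCFI and OS are unaffected. The change should be made, but it concerns a secondary endpoint.

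**What to change.** **Sufficient change (wording in Section 5).**

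1. Exempt the change in ctDNA from enrolment to end of COS from the rule that safety analyses are made against the non-stimulated cohort.
2. Compare that change between the letrozole and standard cohorts, adjusted for baseline ctDNA, days between draws, and breast surgery (none, before the first draw, or between draws).
3. State that this contrast is also Belgium versus France.
4. State that the within-cohort change alone is not evidence for or against an effect of stimulation on ctDNA.

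The cost is a narrower ctDNA claim: protocol against protocol, not stimulation against none. Section 3.2 lists the type of breast surgery but not its date, and does not list the plasma draw dates. The sponsor should confirm that the eCRF holds both, since the adjustment needs them.

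**Optional, at higher cost.** If the month 0-1 sample was meant for all cohorts, say so in Table 1 and Section 4.4 and define its timing before chemotherapy for non-stimulated women. The two contrasts in Section 5 can then be run with the same covariates. Under Section 4.4 this means a further timed draw of two 10 ml plasma tubes, centrifugation within 1 hour, a high-speed spin, storage at -80°C and assay, in up to 339 women. It is the only route to the stated aim, and a pre-chemotherapy sample cannot be recovered once chemotherapy has begun.

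**In either case,** reconcile Table 1 with Section 4.4 on whether plasma is taken at end of follow-up in women who have not relapsed.
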